4.5.2 Lymph Node Level

- The number and percentage ^{e)} of LN with metastatic spread, based on histopathologic review, detected by ASP5354

ISN/Protocol 5354-CL-1201

- The number and percentage ^{e)} of LN with metastatic spread, based on histopathologic review, detected by SoC treatment with either Tc-99mSC or Lymphoseek

- The difference in proportion of LN with metastatic spread, based on histopathologic confirmation of LN tissue between ASP5354 and SoC treatment with either Tc-99mSC or Lymphoseek and 95% CI
 - e) The denominator is the number of LN identified intraoperatively by histopathologic confirmation

4.6 Other Endpoints

4.6.1 Green Coloration of Urine or Skin

The frequency and percentage of patients who experience green coloration of urine will be summarized by dose level and tumor type only for subjects who used urethral catheter. The duration of green coloration of urine or skin (in hours) will be summarized using descriptive statistics by dose level and tumor type. The duration is calculated from first date/time point of green coloration of urine or skin to last date/time point of green skin coloration. If the green coloration of urine or skin is still present at discharge, the duration is from first date/time point of green coloration to the date/time of discharge.

Additional to descriptive statistics, if applicable, the duration will be analyzed using Kaplan Meier estimation. For this purpose, subjects with green coloration of urine or skin at discharge are censored at the time point of discharge.

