7.2.6 Other Assessments

7.2.6.1 Green Coloration of Urine or Skin

The occurrence of green coloration of the urine or skin will be monitored throughout the study. If observed, any visual green coloration abnormalities will be recorded as an AE. If urine coloration occurs for participants who have a urethral catheter in place, the color of urine will be assessed during surgery and every 120 minutes (\pm 30 minutes window) after the end of surgery until it resolves or the participant is discharged, whichever is earlier. If no urethral catheter is in place, voided urine will be assessed for green coloration and the time collected until it resolves or the participant is discharged, whichever is earlier. The start and stop date and time will also be recorded. The occurrence of green coloration of the skin will be recorded as an AE any time after dose administration. The start and stop date and time will be recorded. Skin coloration will be followed up until it resolves or the participant is discharged, whichever is earlier.

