9.3.5 Safety Analyses

The safety and tolerability will be summarized by descriptive statistics for the safety analysis set (SAF) population. The SAF population consists of all participants who received ASP5354.

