9.3.5.1 Adverse Events

AEs will be coded using MedDRA and graded using the National Cancer Institute-Common Terminology Criteria for Adverse Events (NCI-CTCAE version 5.0).

A TEAE is defined as an AE observed after administration of the IP and up to the follow-up period. An IP-related TEAE is defined as any TEAE with a causal relationship assessed as “yes” by the investigator.

The number and percentage of participants with TEAEs, IP-related TEAEs, serious TEAEs, IP-related serious TEAEs and green coloration of urine or skin will be summarized by system organ class, preferred term and dose group. The worst grade will be summarized if the same AE is recorded more than once for a participant.

AE data will be listed.

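### SAP 4.6.1 ends coloration duration at the last green skin time, so resolved urine-only cases have no duration, and its frequency table leaves out voided-urine and skin events

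*SAP*

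**What the plan says.** **Duration (SAP 4.6.1).** The section promises descriptive statistics, in hours, for the duration of green coloration of urine or skin, by dose level and tumor type. The general rule is: "The duration is calculated from first date/time point of green coloration of urine or skin to last date/time point of green skin coloration". There is one other end point. For coloration still present at discharge, "the duration is from first date/time point of green coloration to the date/time of discharge". A Kaplan-Meier analysis is added if applicable, and for it "subjects with green coloration of urine or skin at discharge are censored at the time point of discharge".

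**Frequency (SAP 4.6.1).** The frequency and percentage of patients with green urine "will be summarized by dose level and tumor type only for subjects who used urethral catheter". The section has no frequency for skin.

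**Protocol, data collection.** Section 7.2.6.1 makes any observed green coloration of urine or skin an adverse event. Catheter urine is checked during surgery and then every 120 minutes (±30). For participants without a catheter: "If no urethral catheter is in place, voided urine will be assessed for green coloration and the time collected until it resolves", or until discharge if that is earlier. On times, it says: "The start and stop date and time will also be recorded". The same is required for skin.

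**Protocol, analysis.** Section 9.3.5.1 plans the number and percentage of participants, stating that "green coloration of urine or skin will be summarized by system organ class, preferred term and dose group". Section 9.3.5 sets the population: "The SAF population consists of all participants who received ASP5354". SAP 4.7.1 carries over the other items of the 9.3.5.1 summary but does not name green coloration.

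**The concern.** There are two separate faults. The first is internal to the SAP: the start of the duration refers to either site and the end to skin alone, so the rule has no answer for coloration seen only in urine. The second is between documents: the coloration table covers fewer participants and fewer events than the protocol's own summary.

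The undefined pattern is a plausible one. The protocol's summaries of the two phase 1 studies report green urine and no green skin (2.2.1.2.1.2 and 2.2.1.2.2.2); skin color change is reported only in rats and monkeys (2.2.2). Those clinical data are intravenous, so skin coloration after local injection remains possible. If cases here are urine-only, the only durations the rule can produce belong to participants still green at discharge. The summary would then rest entirely on the unresolved cases. The urine table would also omit every event seen in voided urine.

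**Working it through.** The documents state no figure for coloration duration or frequency, so there is none to reproduce. The check applies the written rules to each possible case. All times and counts below are constructed.

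**1. Single cases, resolved before discharge (hours after dosing).** SAP duration = last green skin time − first green time at either site. True duration = last green time − first green time, over both sites.

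| Case | SAP 4.6.1 | True |
|---|---|---|
| Urine only, 1 to 9 | undefined (no skin time) | 9 − 1 = 8 h |
| Urine 1 to 9, skin 1 to 4 | 4 − 1 = 3 h | 9 − 1 = 8 h |
| Urine 1 to 4, skin 1 to 9 | 9 − 1 = 8 h | 8 h |
| Skin only, 1 to 9 | 9 − 1 = 8 h | 8 h |

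In the second row the rule loses 8 − 3 = 5 h. Coloration still present at discharge is defined in every pattern and is not in question.

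**2. A group of five urine-only cases.** Four resolve after 2, 4, 6 and 8 h; one is still green at discharge, at 10 h.

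- *SAP rule.* The four resolved cases have no end time and no censoring rule applies to them. What remains is n = 1, duration 10 h; Kaplan-Meier has 0 events and no estimable median.
- *Same-site rule.* n = 5; mean (2 + 4 + 6 + 8 + 10)/5 = 6 h; median 6 h. Kaplan-Meier has 4 events and 1 censored: S(2) = 4/5 = 0.80; S(4) = 0.80 × 3/4 = 0.60; S(6) = 0.60 × 2/3 = 0.40. The median is 6 h.

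**3. Incidence.** Assume 6 of 12 dosed participants at one dose level have green urine, so the figure in the safety analysis set is 6/12 = 50%. The documents give no catheter share, so let k of the 12 have a catheter. The number of green cases among catheter users then lies between max(0, 6 − (12 − k)) and min(k, 6).

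| Catheter users k | Green among them | Percentage in the 4.6.1 table |
|---|---|---|
| 0 | none | not computable |
| 3 | 0 to 3 | 0 to 100% |
| 6 | 0 to 6 | 0 to 100% |
| 9 | 3 to 6 | 33 to 67% |
| 12 | 6 | 50% |

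These are bounds, not forecasts. A participant with green skin only is never counted as an event in this table, whatever k is.

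**4. The two frequency plans side by side.** Protocol 9.3.5.1 covers urine or skin, in all who received ASP5354, by dose group. SAP 4.6.1 covers urine, in catheter users, by dose level and tumor type. SAP 4.6.1 also differs within itself: its duration sentence covers either site with no catheter limit, so the participants in its two tables need not match.

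**The case against.** The strongest reply is that the duration fault is a slip in one phrase. Everywhere else in SAP 4.6.1 the duration, discharge and censoring rules refer to urine or skin, or to coloration without a site, and the SAP version history records a wording replacement in this section. The stop times for both sites are collected. That is probably how the error arose, but a programmer must either follow the text or guess, and two readings are open: a duration for each site, or one combined duration.

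On incidence, coloration is an adverse event with or without a catheter, and SAP 4.7.1 tabulates all TEAEs by preferred term in the safety analysis set and lists AE data. This stands, and it is the main reason the point is minor. It does not supply a duration or correct a dedicated table that omits voided-urine and skin events. Limiting that table to catheter users, whose urine is checked on a schedule, could be deliberate, but no reason is given.

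The SAP also appears to lag the protocol. Its version history cites Protocol Amendment 2 for this section, and it still defines a pharmacokinetic analysis set that the current protocol does not have. That may explain the mismatch; the two texts still need reconciling.

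Finally, the evidence for green urine is dose-dependent. In the intravenous studies it was reported at 2 mg and above and was absent at 0.5 mg. The initial dose levels here run from 0.05 to 1 mg, and 2 and 4 mg open only conditionally. Few or no urine events may occur at the lower doses. This limits how often the gap would matter; it does not define the missing case.

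**Conclusion.** The concern holds, and it is minor. As written, SAP 4.6.1 gives no duration for urine-only coloration that resolves before discharge and too short a duration when urine outlasts skin. Its frequency table excludes voided-urine events and gives no skin frequency, which does not match Protocol 9.3.5.1. The duration fault is not a conflict with the protocol, because the current protocol plans no duration analysis.

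The size cannot be estimated for this trial, since the documents give neither a catheter share nor a coloration rate after local injection. The constructed examples show only what the rules do: a 5 h loss in one mixed case, four of five durations lost in a urine-only group, and a percentage that catheter use could move anywhere from 0 to 100% around a true 50%. No hypothesis is tested, and the events should remain visible in the TEAE tables and the AE listing.

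**What to change.** In SAP 4.6.1:

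- Define duration separately for urine and for skin, each from the first to the last green time at the same site, or to discharge if still present, with Kaplan-Meier censoring by site to match. Alternatively, delete the duration analysis, which Protocol 9.3.5.1 and 9.3.7 do not call for.
- Report urine and skin incidence as separate rows in the safety analysis set, by actual dose received as SAP 4.1 requires, with catheter status as an optional subgroup line.

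In SAP 4.7.1, add green coloration of urine or skin to the items summarized, to match Protocol 9.3.5.1.

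The cost is SAP wording and one or two extra table rows, with sparse cells at low doses. No new data are needed: catheter urine, voided urine and skin are already assessed, and start and stop times are already recorded.

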1.3.1 Sample Collection and Timed Procedure Schedule

Table 2 Sample Collection and Timed Procedure Schedule

Day	Operation	Time Point	Sample Collection	Collection Window
			Blood Sampling for Pharmacokinetics	
Day 1	Preoperative	Predose	X	Within 1 h before dosing
		10 min ^a	X	5 min \leq and < 15 min
	Intraoperative	30 min ^a	X	15 min \leq and < 45 min
		60 min ^a	X	45 min \leq and < 75 min
		90 min ^a	X	75 min \leq and < 105 min
	End of surgery ^b	-	X	-

h: hour

a. If the end of surgery is earlier than this time point, this time point(s) will not need to be collected.

b. In case the participant needs other surgery following sentinel lymph node biopsy, this time point will be at the time of all surgeries end.

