Participants will receive Tc-99mSC or Lymphoseek as part of SoC for SLN biopsy. In case the participant needs other surgery (e.g., lumpectomy, mastectomy etc.) on the same day of study drug administration, the other surgery is allowed once the SLN biopsy has completed. In the operating room, participants will receive ASP5354. After administration of ASP5354, visualization of the LN(s) will be assessed using a NIR-F imaging system followed by confirmation with the gamma probe. Once lymphatic mapping is completed, gamma probe will be used per SoC. For all the LNs observed by ASP5354, gamma probe will be attempted to measure radioactivity. If the LN is not observed with NIR-F after approximately 15 minutes following injection for breast cancer participants and approximately 15 to 30 minutes for melanoma participants depending on the location of the tumor and LNs, the investigator can proceed to use the gamma probe for LN detection. When the LN is detected with the gamma probe first, radioactivity will be measured and then NIR-F imaging should be attempted again for LN visualization. For participants with melanoma, usage of lymphoscintigraphy or SPECT as part of SoC is also allowed.

The visualization data to be collected will consist of the following:

- The visualization of the LN(s) will be assessed by the investigator intraoperatively using a binary “Yes or No” question.
 - If “Yes,” the time of surgical identification of LN(s) will be collected by the investigator.
 - If “Yes,” the number of LNs visualized and the number of LNs visualized with histopathology confirmed LN will be also assessed by the investigator.
Note: Histopathology review will be conducted per standard practice at each site.
- Transdermal visualization of lymphatic spread of ASP5354 after injection of the drug will also be assessed using a binary “Yes or No” question.
- The fluorescence intensity of the LN will be qualitatively assessed using a Likert Scale (0 = None; 1 = Mild; 2 = Moderate; and 3 = Strong).
- The radioactivity count will be collected for all the LNs identified by ASP5354 and/or SoC.
- The number of LN(s) with metastatic spread will be assessed based on histopathologic review.
Note: Histopathology review will be conducted per standard practice at each site.

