ASP5354 will be injected subcutaneously at a minimum of 2, and up to 4. sites of equally divided subareolar injections. Please refrain from massaging the area of drug administration. After approximately 5 to 10 minutes, lymphatic mapping will then occur based on intraoperative fluorescence visualization using ASP5354. LNs will be identified by NIR-F imaging, followed by identification with the gamma probe. In the event that NIR-F imaging does not detect LN after approximately 15 minutes, the gamma probe should be used for LN identification. When the LN is detected with the gamma probe first, NIR-F imaging should be attempted again for LN visualization. Dissection of the LN will be conducted following identification by NIR-F imaging and/or the gamma probe. Before completing the surgery, NIR-F imaging and the gamma probe will be used to confirm further presence of other LNs, with further dissection and LN removal if indicated.

Melanoma

Arm/ IP Name	Melanoma 0.05 mg/ ASP5354	Melanoma 0.2 mg/ ASP5354	Melanoma 0.6 mg/ ASP5354
Use	test product	test product	test product
Dose	0.05 mg	0.2 mg	0.6 mg
Concentration	1.0 mg/mL	1.0 mg/mL	1.0 mg/mL
Volume	0.05 ml in total	0.2 ml in total	0.6 ml in total
Frequency	single dose	single dose	single dose
Route	intradermal injection	intradermal injection	intradermal injection
Location	peritumoral	peritumoral	peritumoral
Injection site	Minimum of 2, up to 4, sites equally divided injections	Minimum of 2, up to 4, sites equally divided injections	Minimum of 2, up to 4, sites equally divided injections
Duration	single dose	single dose	single dose

Arm/ IP Name	Melanoma 1 mg/ ASP5354	Melanoma 2 mg/ ASP5354
Use	test product	test product
Dose	1 mg	2 mg
Frequency	single dose	single dose
Concentration	1.0 mg/mL	1.0 mg/mL
Volume	1.0 mL in Total	2.0 mL in total
Frequency	single dose	single dose
Route	intradermal injection	intradermal injection
Location	peritumoral	peritumoral
Injection site	Minimum of 2, up to 4, sites equally divided injections	Minimum of 2, up to 4, sites equally divided injections
Duration	single dose	single dose

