ASP5354 will be injected intradermally at a minimum of 2, and up to 4, sites of equally divided peritumoral injections. Please refrain from massaging the area of drug administration. After approximately 5 to 10 minutes, lymphatic mapping will occur based on intraoperative fluorescence visualization using ASP5354. LNs will be identified by NIR-F imaging, followed by identification with the gamma probe. Please note that the time from injection of IP to the first visualization may vary due to tumor and LN location. In the event that NIR-F imaging does not detect LN after approximately 15 to 30 minutes, the gamma probe should be used for LN identification. When the LN is detected with the gamma probe first, NIR-F imaging should be attempted again for LN visualization. Dissection of the LN will be conducted following identification by NIR-F imaging and/or the gamma probe. Before completing the surgery, NIR-F imaging and the gamma probe will be used to confirm further presence of other LNs with further dissection and LN removal if indicated.

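### SAP 4.6.1 has no rule for stained skin removed by same-day surgery, so excision counts as an observed end of coloration and shortens stain duration

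*SAP*

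**What the plan says.** Protocol 4.1 permits further surgery on the dosing day after the node biopsy: "In case the participant needs other surgery (e.g., lumpectomy, mastectomy etc.) on the same day of study drug administration, the other surgery is allowed". Protocol 6.1.1 places the injection at 2 to 4 "sites of equally divided subareolar injections" in breast cancer and at 2 to 4 "sites of equally divided peritumoral injections" in melanoma.

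Protocol 7.2.6.1 treats green skin as an adverse event: "The occurrence of green coloration of the skin will be recorded as an AE any time after dose administration". Start and stop times are recorded, and "Skin coloration will be followed up until it resolves or the participant is discharged, whichever is earlier". It has no instruction for stained skin that is cut out.

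SAP 4.6.1 plans descriptive statistics for duration by dose level and tumor type, and Kaplan-Meier estimation where applicable. Duration runs "to last date/time point of green skin coloration". If coloration is still present at discharge, the descriptive duration stops at discharge; for Kaplan-Meier, "subjects with green coloration of urine or skin at discharge are censored at the time point of discharge". No other censoring reason is given, and neither document mentions an excised injection site.

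**The concern.** A mastectomy that takes the areola, or an excision of a melanoma site, can remove the skin that was injected. If that was the only stained skin, the last green time falls no later than the excision and no green skin is left at discharge. The participant then looks like someone whose stain faded quickly.

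This matters because Protocol 2.3.2 names skin staining among the drawbacks of existing agents, and the human studies summarized in Protocol 2.2.1.2 used intravenous dosing, so persistence of local staining is new information here. Dose levels are also filled in sequence without randomization (Protocol 4.1 and 6.3). The share of participants with the site removed can therefore differ between dose levels, and a difference in stain duration could reflect surgery and not dose.

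**Working it through.** The documents state no figure for excision, staining or discharge time, so there is nothing of the plan's own to reproduce. The check has two parts.

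**1. Applying the rule to an excised stain**

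- Duration ends at the last green-skin time (SAP 4.6.1). With the only stained skin removed, that is at or before excision.
- Censoring requires coloration at discharge (SAP 4.6.1). There is none.
- The record is therefore an uncensored, short duration. The descriptive summary takes in the same short value, so the effect does not depend on Kaplan-Meier being used.

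**2. Illustration of size**

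From the documents: at most 12 participants per dose level (Protocol 9.5). Assumed: all 12 are stained, k are excised 2 h after staining starts, and the rest are still stained at discharge, at 24 h or 6 h.

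- Kaplan-Meier proportion still stained just before discharge, excision counted as an end: 1 − k/12. With excision censored there are no events, so it is 1.00.
- Mean duration as written, discharge at 24 h: (2k + 24(12 − k))/12.
- Mean duration as written, discharge at 6 h: (2k + 6(12 − k))/12.

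| k excised | KM as written | KM, excision censored | Mean, discharge 24 h | Mean, discharge 6 h |
|---|---|---|---|---|
| 0 | 1.00 | 1.00 | 24.0 h | 6.0 h |
| 3 | 0.75 | 1.00 | 18.5 h | 5.0 h |
| 6 | 0.50 | 1.00 | 13.0 h | 4.0 h |
| 9 | 0.25 | 1.00 | 7.5 h | 3.0 h |

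The retained-site mean is 24 h or 6 h throughout. It is itself cut off at discharge, so it is a lower bound on true staining time.

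A second version lets stains fade. Assume exponential fading with median m, a fraction f excised 0.5 to 1.5 h after onset, and discharge at 6 h. The true share faded by 4 h is p = 1 − 2^(−4/m); as written the share is f + (1 − f)p.

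- m = 24 h: p = 10.9%. As written: 20%, 33%, 55% and 78% for f = 10%, 25%, 50% and 75%.
- m = 6 h: p = 37.0%. As written: 43% at f = 10% and 84% at f = 75%.
- Standard error at n = 12, √(p(1 − p)/12): 9.0 points for m = 24 h and 13.9 points for m = 6 h. At f = 10% the shift is 8.9/9.0, about 1.0 standard error, or 6.3/13.9, about half a standard error.

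The direction is the same in every case. The size ranges from minor to dominant, depending on inputs that the documents do not supply.

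**The case against.** The strongest reply is that the target is undefined. The protocol states that no estimand is defined, and one could describe how long patients were visibly stained under actual surgical care; removed skin no longer stains anyone. But the SAP censors at discharge. That makes sense only if the target is time until the stain resolves, and surgical removal is not resolution.

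Several further points stand and lower the weight:

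- Duration sits under other endpoints, and Kaplan-Meier is conditional. Protocol 9.3.5.1 reports green coloration by number and percentage, and 9.3.7 plans no duration analysis. The SAP still does.
- No passage says that excision equals resolution; this follows from applying the rule. Site instructions on stop times could sit in the eCRF Completion Guideline, which is not among the documents.
- Lumpectomy need not remove areolar skin, and melanoma excision is covered only by the open-ended part of the list in Protocol 4.1.
- Preplanned and elective procedures are already collected in the eCRF (Protocol 7.3.5), so excision may be derivable.

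Two stronger readings are tempting. A reader might infer that local reactions at an excised site count as absent. The documents do not support that: reactions and stains seen before excision remain treatment-emergent events (Protocol 7.2.6.1, SAP 4.7.1). Only reactions that would first appear afterwards are unobservable. A reader might also infer that the plasma concentrations are distorted. Table 2, footnote b, provides for further surgery ("In case the participant needs other surgery following sentinel lymph node biopsy, this time point will be at the time of all surgeries end"), concentrations are only described, and nothing in the documents shows that excision changes them.

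**Conclusion.** The gap is real and narrow. As written, SAP 4.6.1 counts excision of the only stained skin as an observed end of coloration and biases skin-coloration duration downward. The bias at each dose level depends on its excision share, which the documents do not give. With 6 of 12 excised and no natural fading before discharge, the Kaplan-Meier proportion still stained is 0.50 instead of 1.00. With 10% excised and 6 h median staining, the shift is about half a standard error.

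This rests on the surgery actually removing the injected skin, on no other green skin remaining, and on sites recording a stop time at or before excision. Severity is low: the endpoint is descriptive, no hypothesis is tested, and staining is not a named criterion for the optimal dose, although safety data in general are part of the Visualization Review Committee's assessment.

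**What to change.** - **Data:** record whether the injection site was excised in the same operation, and when. This is one eCRF item, or a derivation from procedure data already collected if those data give site and time.
- **SAP 4.6.1, Kaplan-Meier:** censor skin-coloration duration at excision. This assumes that the surgery was planned for the tumor and not prompted by the stain, which is reasonable here and should be stated.
- **SAP 4.6.1, descriptive summary:** give skin-coloration duration for participants whose site was retained, and show the number excised per dose level and tumor type.
- **SAP 4.7.1:** add a footnote to the local-site-reaction row giving the number with the site retained. As a gauge, the exact upper 95% limit for zero events, 1 − 0.025^(1/n), is 26.5% for 0/12 and 45.9% for 0/6. The second figure is the extreme case, since excised participants were observed until excision. Separate adverse-event tables are not warranted in cohorts of 3 to 12.

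The cost is one data item at most and a few lines of SAP text. The downside is that fewer participants contribute to the duration summary. If the sponsor instead drops the duration analysis from the SAP to match the current protocol, the changes to 4.6.1 are no longer needed.
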